2.1 Study Objectives and Design

1.0 * Provide a lay summary of your proposed research which would be understandable to general public

Inguinal hernia repair is one of the most common surgeries, with more than 20 million performed globally each year. It is estimated that approximately 15% of patients undergoing inguinal hernia repair will experience persistent post-surgical pain that could last months to years. Evidence from related procedures indicates that better surgical preparation through pre-operative exercise and education (i.e. Prehabilitation) followed by ongoing post-surgical rehabilitation leads to more rapid recovery, return to activities and lower likelihood of persistent post-surgical pain. We will determine the feasibility of a peri-operative rehabilitation program (pre- and post-surgery)

and our study protocol for patients undergoing inguinal hernia repair surgery. We hypothesize that: 1) our peri-operative intervention will be feasible and safe to undertake within a clinical setting; 2) we will enrol adequate numbers to justify a larger trial; and that 3) our outcome measurement protocol will provide meaningful information with high response rate and low attrition after 3 months.

Implications

This study is novel and timely given the current healthcare focus on improving strategies for the prevention of chronic pain. The obvious potential benefits for patients with inguinal hernia is the development of a program with the potential to improve post-surgical outcomes and reduce likelihood of post-surgical pain. Our findings will inform a larger, multicenter clinical trial to evaluate this intervention approach in patients undergoing inguinal hernia repair.

2.0 * Provide a full description of your research proposal outlining the following:

- Purpose
- Hypothesis
- Justification
- Objectives
- Research Method/Procedures
- Plan for Data Analysis

Purpose

The aim of the proposed project is to determine the feasibility of a perioperative rehabilitation program (pre- and post-surgery) and our study protocol for patients undergoing inguinal hernia repair surgery. We will answer the following question: Is a study of a peri-operative rehabilitation program feasible in terms of recruitment rate, treatment adherence, timelines, data collection procedures, patient follow-up and resources required?

Hypothesis

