We hypothesize that: 1) our peri-operative intervention will be feasible and safe to undertake within a clinical setting; 2) we will enrol adequate numbers to justify a larger trial; and that 3) our study protocol will provide meaningful information with high response rate and low attrition after 3 months.

Justification

Inguinal hernia repair is one of the most common surgeries performed globally, with more than 20 million performed each year.[1] Not only does this huge number of surgeries have a substantial direct economic burden on healthcare systems, there is also indirect impact from time off work and decreased productivity due ongoing post-surgical pain requiring extended time spent on modified duties. It is estimated that approximately 15% of patients undergoing inguinal hernia repair will experience persistent post-surgical pain that could last months to years.[2, 3] Furthermore, current clinical guidelines for return to work and activity after inguinal hernia repair are inconsistently informed by evidence, highly variable, and outdated.

[4] Forbes et al (2012) found that the average patient undergoing inguinal hernia repair experiences more than 40 days of short-term disability despite indications that earlier return to activity is safe (i.e. will not lead to repair failure) and likely beneficial for reducing chronic pain and disability.[4]

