Intervention Description - The perioperative rehabilitation program will include an established set of structured exercises aimed at core strengthening and individualized activity-based functional training in preand post- operative stages. We will follow a traditional occupational rehabilitation approach, focusing exercise training on activities that the patient is experiencing difficulty with due to the hernia. The exercise program is described in more detail in the attached 'hernia exercise protocol' document. The program will be delivered by a physiotherapist and a trained exercise therapist. This includes the sessions that will be done in person as well as those that will be done virtually. Education that will be provided includes basic information about inguinal hernia and the surgical repair technique, what to expect in the days and weeks following surgery, advice for post-operative recovery, importance of activity and exercise to recovery, pain coping strategies and techniques for reducing risk of hernia recurrence. Education will be provided in person by the surgeon and study team, as well as through YouTube videos that provide more standardized information. Education that will be provided includes basic information about inguinal hernia and the surgical repair technique, what to expect in the days and weeks following surgery, advice for post-operative recovery, importance of activity and exercise to recovery, pain coping strategies and techniques for reducing risk of hernia recurrence.

Measures – In additional to demographic and occupational information, we will collect feasibility and clinical outcomes. Feasibility outcomes are: 1) recruitment rate expressed as the average number of patients referred to the study per week and the number of participants enrolled in the program; 2) patient adherence to the program; 3) acceptability of program content; 4); acceptability and compliance with study questionnaires; 5) follow-up rates; and 6) serious adverse events. A priori criteria for the feasibility outcomes are presented in the Appendix.

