Clinical outcomes will be collected at baseline, before surgery, and following the post-surgical intervention by a researcher not involved in the delivery of the intervention. Persistent post-surgical will be defined as pain lasting longer than 3 months post-surgery as per the IASP definition.[15] We will measure pain intensity ratings on a 0-10 Numeric Pain Scale. We will also measure pain-related disability using the Pain Disability Index and SF-12 measures. Lastly, after the operation we will administer the hernia-specific Carolinas Comfort Scale (CCS).[16] The CCS is a widely used hernia-specific patient reported outcome measure that focuses on mesh-related symptoms.[17] We will also measure quality of life and factors linked to chronic pain such as coping strategies, catastrophizing and Kinesiophobia.

Safety and adverse effects – At the weekly sessions, we will as about both exercise completion as well as any symptoms or adverse events experienced. These will be documented. Any post-surgical complications severe enough to warrant referral to the surgeon or ultrasound imaging will also be tracked. Since the ultrasounds are only being done to rule out hernia recurrence as part of routine clinical care, this will be done and interpreted by a radiologist. All patients will also undergo a consult with the surgeon at 1-week, 1-month, and 3-month follow-up as per usual practice.

Plan for Data Analysis

A sample size of 30 participants will yield confidence intervals whose lower limits can help define the range of plausible values for a subsequent power analysis program. This will guarantee the timely and on-budget completion of the study. All analyses will be conducted using STATA 14.2. Descriptive analysis will be used to report feasibility outcomes (e.g. recruitment rates, adherence, etc.) and identify trends of clinical outcomes. Feasibility targets will be evaluated as per the Appendix.

See Attached Study Protocol for the full list of references.

- 3.0 Describe procedures, treatment, or activities that are above or in addition to standard practices in this study area (eg. extra medical or health-related procedures, curriculum enhancements, extra follow-up, etc): The Prehab program discussed above that we are studying is in addition to the standard surgical practices in this study area.

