Format Acceptability							
50% found treatment delivery (in-person and home) acceptable (Likert ≥ 4/5)	25% found treatment delivery acceptable (Likert ≥ 4/5)	< 25% found treatment delivery acceptable (Likert ≥ 4/5)					
50% reported being likely to recommend this treatment	25% reported being likely to recommend this treatment	< 25% reported being likely to recommend this treatment					
50% reported being likely to use this treatment again	25% reported being likely to use this treatment again	< 25% reported being likely to use this treatment again					

Follow Up						
90% of participants followed up at the end of Prehab	50% of participants followed up at the end of Prehab	25% of participants followed up at the end of Prehab				
80% of participants followed up at 3 months	50% of participants followed up at 3 months	25% of participants followed up at 3 months				
Treatment						
70% of participants attended all treatment sessions	50% of participants attended all treatment sessions	25% of participants attended all treatment sessions				
70% of sessions were compatible with participant's work/activity schedule	50% of sessions were compatible with participant's work/activity schedule	25% of sessions were compatible with participant's work/activity schedule				
Burden						
75% of participants found the burden of completing questionnaires Likert <3/10 (0 = no burden, 10 = most burden)	50% of participants found the burden of completing questionnaires Likert <3/10 (0 = no burden, 10 = most burden)	25% of participants found the burden of completing questionnaires Likert <3/10 (0 = no burden, 10 = most burden)				
Adverse Events						
No adverse event	1 adverse event related to re- injury	2 or more adverse events

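### Does the 3-month follow-up target in Appendix 2 need its own questionnaire-completion criterion?

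*Combined protocol and SAP*

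**What the plan says.** Section 2.1, item 2.0 (Measures) numbers six feasibility outcomes. The fourth and fifth are listed separately: "acceptability and compliance with study questionnaires; 5) follow-up rates". Neither carries a time point. The same paragraph states that "A priori criteria for the feasibility outcomes are presented in the Appendix", and the Plan for Data Analysis repeats this: "Feasibility targets will be evaluated as per the Appendix".

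Hypothesis 3 appears twice in section 2.1. The lay summary says that "our outcome measurement protocol will provide meaningful information with high response rate and low attrition after 3 months"; the full proposal has "our study protocol will provide meaningful information with high response rate and low attrition after 3 months". Neither attaches a number.

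Appendix 2 is where the numbers are. Its Follow Up block has one row for the end of Prehab (90% to proceed) and one for 3 months: "80% of participants followed up at 3 months" to proceed, 50% to proceed with amendments, 25% for significant amendments. The only row that mentions questionnaires is Burden, which scores how burdensome they felt.

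On timing, section 2.1 says "Clinical outcomes will be collected at baseline, before surgery, and following the post-surgical intervention". Under Safety and adverse effects it adds: "All patients will also undergo a consult with the surgeon at 1-week, 1-month, and 3-month follow-up as per usual practice".

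**The concern.** Two things look wrong. First, the text promises a criterion for questionnaire compliance, and the Appendix seems not to contain one: Burden covers the acceptability half of that outcome but not the compliance half. Second, the row that could fill the gap leaves its event undefined. The only contact that the supplied text places by name at 3 months is the surgeon consult, which would take place without the trial.

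This trial exists to judge feasibility. If consult attendance satisfied the 3-month row, the trial could be judged ready to proceed while few pain, disability and quality-of-life forms had come back. The next trial's attrition allowance might then rest on attendance and be too small.

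**Working it through.** **Inputs.** N = 30, 15 per arm (sections 2.1 and 4.2). Thresholds of 80% and 50% (Appendix 2). The documents give no attendance rate, return rate or dropout assumption, so every rate below is an assumption.

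**The plan's figure as a count.** 0.80 × 30 = 24 and 0.50 × 30 = 15. An observed 24/30 has an exact (Clopper-Pearson) 95% interval of 61.4% to 92.3%. The 80% is a chosen threshold, so there is no derivation to reproduce.

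**Could the two readings give different verdicts?** Yes, under suitable assumptions.
- Suppose 27 of 30 attend the consult and 18 of 30 return the final questionnaire. Then 27/30 = 90% meets the target, while 18/30 = 60% (exact 95% interval 41% to 77%) falls in the amendments band.
- Suppose instead true rates of 90% and 70%. With X ~ Binomial(30, p), P(X ≥ 24) = 0.974 at p = 0.90 and 0.160 at p = 0.70.

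So the definition matters if the consult reading is a live one. The text decides that.

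**Which reading does the text support?**
1. *Companion row.* The Follow Up block uses the same verb for the end of Prehab and for 3 months. The routine consults are at 1 week, 1 month and 3 months after the operation, so none falls at the end of Prehab. The pre-surgery research collection does. Attendance at treatment sessions has a separate row. In the first row, then, followed up means a research assessment, and the same words one line down should mean the same.
2. *Section 5.2 (Data Identifiers).* Address and postal code are collected, and identifiers kept, so that the team can reach participants for follow-up. That describes research contact, not a routine surgical visit.
3. *Hypothesis 3.* The lay summary makes the outcome measurement protocol the thing that should show low attrition after 3 months. Consult attendance cannot test that.

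**What the row covers on that reading.** The outcomes in section 2.1 are largely self-report scales: numeric pain rating, Pain Disability Index, SF-12, Carolinas Comfort Scale, coping, catastrophizing and kinesiophobia. Section 2.9 has questionnaires completed in REDCap, with paper as a fallback. To be followed up for research is therefore, in practice, to return the questionnaire. Of 30, the target then allows at most 30 − 24 = 6 missing. Burden covers acceptability; Follow Up covers response.

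**Do the downstream figures follow from the wording?**
- *Enrolment factor.* With the assumed counts, 1/0.90 = 1.11 against 1/0.60 = 1.67, so a trial planned on attendance would obtain 0.60/0.90 = 67% of its intended outcome data. That requires the planners to ignore their own count of returned questionnaires.
- *Variance precision.* The upper 95% limit on a variance pooled over two arms is df/χ²(0.025, df) times the estimate, with df = n − 2: 2.00 for 24 completers and 2.32 for 18. This depends on how many forms come back, which the definition of an Appendix row does not change.

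**The case for a change.** The strongest case for a change is that a progression criterion is useful only if fixed before the data are seen. Section 2.1 lists compliance and follow-up as two outcomes and sends both to the Appendix, so a reader may expect two criteria. The plan itself uses the word follow-up for the surgeon's 3-month consult and attaches no month to the last research collection. Clarifying it would cost one sentence.

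Part of this stands. Appendix 2 contains no explicit completion row and no definition of the event, and nothing says how a partly completed questionnaire counts. The attached data collection timeline named in section 2.1 is not among the supplied documents. It may settle the point, but that cannot be assumed.

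What does not stand is the step from an unwritten definition to a misleading decision. It needs the less natural reading of one row, against its companion row, section 5.2 and hypothesis 3. It also needs investigators who report consult attendance in place of the research data that the pilot was set up to collect.

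**Conclusion.** The wording is incomplete, but no change to the plan is required. An analyst would take followed up at 3 months to mean that the scheduled research questionnaire was completed, would count it over all randomised participants, and would use that row for the compliance half of the fourth outcome and the response rate in hypothesis 3. Writing this down would be a courtesy to readers. It would not alter the design, the sample size or the descriptive analysis.

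The reach is small: one progression row, half of one feasibility outcome and one hypothesis, in a 30-person pilot that specifies only descriptive analysis. No numerical consequence is established, because every attendance and return rate used above is assumed. The conclusion rests on reading the two Follow Up rows alike and on the outcomes being mainly self-report. It would weaken if the attached timeline scheduled no research questionnaire around 3 months; nothing in the supplied text suggests that.

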Specific physical complications could arise before the operation is performed or after surgery. Prior to surgery, the patient may experience more pain in the hernia site as well as normal pain associated with exercise, they may notice worsening of the size of the hernia, and there is a very small chance of hernia incarceration (i.e. herniated tissue becomes trapped and cannot easily be moved back into place – typically occurs in less than 1% (0.18% to 0.79%) of hernia cases). Increased symptoms or size of the hernia will be monitored, and exercises will be modified if the symptoms become intolerable to the participant. Hernia incarceration is an acute painful episode that will require a visit with the surgeon.

In the post-operative phase, patients may experience postoperative pain, opening of the superficial wound from potential hazards associated with exercising (i.e. falling, etc.). However, studies on the force required to cause hernia rupture indicate the force is quite high and beyond those generated during the exercises prescribed. If a participant experiences pain associated with our exercise intervention, we will modify or stop the aggravating exercises after consultation with the surgeon.

Exercise prior to surgery requires mental concentration and participants may feel psychologically or emotionally stressed or fatigue. Since they are in a research study, there is always some risk of social risk through loss of privacy.

4.0 * Describe how you will manage and minimize risks and discomforts, as well as mitigate harm:

The exercise programs will be monitored by experienced physical therapists and kinesiologists who will track patient progress. Since the exercise program is overall low intensity exercise, we do not anticipate many injuries or adverse events. However, if patients begin experiencing problems, the therapists will advise on alterations to make the exercises less intensive or recommend that the program be stopped. The therapists will also be available should more serious adverse events occur such as injury or other related complication. If this occurs, the therapists will advise on self-management strategies for the injury or initiate follow-up with the surgeon.

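### The Appendix adverse-event row scores a different class of event from the serious adverse events named as the outcome, and leaves a single event not related to re-injury without a tier

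*Combined protocol and SAP*

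**What the plan says.** Section 2.1, Measures, lists six feasibility outcomes. The list ends "5) follow-up rates; and 6) serious adverse events", and the next sentence reads "A priori criteria for the feasibility outcomes are presented in the Appendix". The Plan for Data Analysis in the same section repeats the link: "Feasibility targets will be evaluated as per the Appendix".

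The matching row of Appendix 2 (Feasibility and Acceptability Criteria, Adverse Events) has three cells:

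- Proceed: no adverse event.
- Proceed with Protocol Amendments: "1 adverse event related to re- injury".
- Significant Amendments Required: "2 or more adverse events".

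On collection, the Safety and adverse effects paragraph of section 2.1 says "At the weekly sessions, we will as about both exercise completion as well as any symptoms or adverse events experienced", and adds "Any post-surgical complications severe enough to warrant referral to the surgeon or ultrasound imaging will also be tracked". Section 3.1, item 4.0, first says that few injuries or adverse events are expected. It then deals separately with what happens "should more serious adverse events occur such as injury or other related complication".

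**The concern.** The outcome and its criterion should describe the same thing. Here the outcome is limited to serious events and the criterion is not. Within the row, the type of event also changes from cell to cell: any event in the first, a re-injury event in the second, any event again in the third.

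At stake is the row's use as a rule set in advance. It is the only safety row in the Appendix, and the first hypothesis is that the intervention is feasible and safe. If the row is applied as written, ordinary exercise-related complaints can place the study in the worst tier although no serious event has occurred. One possible result cannot be placed at all.

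**Working it through.** The row contains no computed figure, so the main check is logical.

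**Step 1: compare the terms.** The outcome in Measures is serious adverse events. The row heading and all three cells say adverse event without that limit. Section 3.1, item 4.0, treats more serious events as a class apart, so the two terms are not used there as synonyms.

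**Step 2: enumerate the row.** Let r be the number of re-injury events and o the number of other events, each from 0 to 2. This gives nine combinations.

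| r | o | Tier as written |
|---|---|---|
| 0 | 0 | Proceed |
| 1 | 0 | Proceed with Protocol Amendments |
| 0 | 1 | none |
| the other six, r + o of 2 or more | | Significant Amendments Required |

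One of the nine has no tier: a single event that is not a re-injury.

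**Step 3: two minor events unrelated to re-injury.** Here r = 0 and o = 2, so the row as written returns Significant Amendments Required. The count of serious events is zero, so a row scored on the named outcome returns Proceed. The same data give opposite ends of the scale.

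**Step 4: one pre-operative incarceration.** Section 3.1, item 3.0, lists this as a possible complication. Suppose that it is not classed as a re-injury. If all events count, then r = 0 and o = 1, and there is no tier. If only serious events count and this one is serious, the count is still one and the middle cell still requires re-injury, so again there is no tier.

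**Step 5: illustration of size.** The documents give no overall adverse-event rate, so the risks below are assumptions. Take n = 15 (one arm, section 2.1, Sample Size) and let X be the number of participants with at least one event, binomial with risk p:

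P(X ≥ 2) = 1 − (1 − p)^15 − 15p(1 − p)^14

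- Any event, p = 0.10: 1 − 0.206 − 0.343 = 0.451, or 45%.
- Serious event, p = 0.01: 1 − 0.860 − 0.130 = 0.010, or 1.0%.

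With any-event risks of 5% and 20%, the first figure becomes 17% and 83%. The contrast comes from the assumed rates. It shows how far the choice of event class can move the result, not what this trial will observe.

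**The case against.** The strongest reply is that re-injury was meant to govern the whole row. Section 3.1, item 4.0, gives this some support, because its examples of more serious events begin with injury. On that reading the gap closes: a single unrelated event falls under Proceed, and so do two minor unrelated events. But the row does not say this. The same sentence also includes other related complications, so a row about re-injury alone would still not measure serious adverse events.

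A second reply is that the list of documents at the end of the application includes a full proposal, a data collection timeline and an adverse events form. None of these is available here, and they may define the terms, the arm counted or the time window. This stands as a limit on the point. A reader might infer that the definition is open and could be picked once the events are known, or that arm, counting unit and window were never set. The available text cannot show either. What it does show is that Measures and the row differ in wording, and a definition held elsewhere would not make them agree.

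A third reply is that the consequence is small: a pilot of 30 participants, a descriptive analysis, events documented in any case so that the row could be re-scored, and gaps in other rows (10 to 14 participants recruited in 8 months also has no tier). All of that is correct and limits the weight of the point. It does not make this row usable as written.

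A reader might also infer that counting only serious events would put a single incarceration in the middle tier. Step 4 shows otherwise. That happens only if the re-injury limit is removed as well, which would be a change to the row and not a reading of it.

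**Conclusion.** The point holds and should be fixed. The named safety outcome and its criterion use different event classes, and the row as written has no tier for exactly one event not related to re-injury. Both findings rest on the text alone and need no assumed rate.

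The size is moderate. The row is one of 14, and no rule makes it decisive for the feasibility conclusion. The documents therefore do not support reading this defect as one that invalidates the feasibility assessment. The 45% against 1.0% contrast depends on assumed risks of 10% and 1%, on 15 participants, on independence between them, and on counting participants and not repeat events.

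**What to change.** Before data are reviewed, reconcile the Measures paragraph of section 2.1 with the Adverse Events row of Appendix 2.

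1. Use one event definition, including any limit on relatedness, in the named outcome and in all three cells. The sponsor chooses whether to restrict the row to serious adverse events, with that term defined, or to change the outcome in Measures to the class that the row scores. If an attachment already holds the definition, cite it in the row.
2. Make the tiers contiguous on that definition: zero, exactly one, two or more such events.
3. Report events outside the definition descriptively.

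This changes one Appendix row and one sentence, with no new data collection. Each choice has a downside. If the row is restricted to serious events, minor events no longer affect the tier. If the outcome in Measures is widened instead, two minor events can still return Significant Amendments Required.
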